16.3 Appendix 3: Specific Renal Alert Criteria and Actions and Event Follow-up

Table 16-3 Specific Renal Alert Criteria and Actions

Serum Event		
Serum creatinine increase 25 – 49% compared	Confirm 25% increase after 24-48h	
to baseline	Follow up within 2-5 days	
Acute Kidney Injury: Serum creatinine	Follow up within 24-48h if possible	
increase \geq 50% compared to baseline	Consider study treatment interruption	
	Consider participants hospitalization /specialized	
	treatment	
GFR is <60 ml x min1 x 1.73 m2	Follow up within 24-48h if possible	
	Consider study treatment interruption	
GFR is <30 ml x min1 x 1.73 m2	Follow up within 24-48h if possible	
	Consider study treatment interruption	
Urine Event	•	
Albumin- or Protein-creatinine ratio increase ≥ 2-		
fold (2 x baseline)	Confirm value after 24-48h	
Albumin-creatinine ratio (ACR) \ge 30 mg/g or \ge 3	Perform urine microscopy	
mg/mmol; Protein-creatinine ratio (PCR) ≥ 1g/g or ≥	Consider study treatment interruption / or	
100mg/mmol	discontinuation	
New onset dipstick proteinuria (≥ 3+)	Confirm assessment within 24-48 hours	
	Consider causes and possible interventions	
	Assess serum albumin & serum total protein	
	Consider drug interruption or discontinuation	
	unless other causes are diagnosed and corrected	
New onset dipstick hematuria (≥ 3+), (after	Confirm assessment within 24-48 hours	
excluding menstruation, urinary infection,	Urine sediment microscopy	
extreme exercise, or trauma)	Perform serum creatinine, ACR	
For all renal events:		
Document contributing factors in the eCRF: co-me	edication, other co-morbid conditions, and	
additional diagnostic procedures performed		
Monitor participant regularly (frequency at investig	ator's discretion) until either:	
Event resolution:		
sCr within 10% of baseline		
• protein-creatinine ratio within 50% of baseline,		
• albumin-creatinine ratio within 50% of baseline		
Event stabilization:		
• sCr level with ± 10% variability over last 6 mon	ths	
• protein-creatinine ratio stabilization at a new le	vel with \pm 50% variability over last 6 months	
• albumin-creatinine ratio stabilization at a new l	evel with ± 50% variability over last 6 months.	

Novartis Amended Protocol Version 02 (Clean)	Confidential	Page 158 of 160 Protocol No. CLJN452D12201C

Novartis Amended Protocol Version 02 (Clean)	Confidential	Page 159 of 160 Protocol No. CLJN452D12201C

Novartis

Amended Protocol Version 02 (Clean)

16.5 Appendix 5: The American Heart Association (AHA) Recommended Diet

Optimization of diet can result in a marked triglyceride-lowering effect that ranges between 20% and 50%. Good practices include weight loss, reducing simple carbohydrates at the expense of increasing dietary fiber, eliminating industrial-produced trans fatty acids, restricting fructose and saturated fatty acids, implementing a Mediterranean-style diet, and consuming marine-derived omega-3 PUFA.

American Heart Association (AHA) recommends the following:

Eat a variety of fruit and vegetable servings every day. Dark green, deep orange, or yellow fruits and vegetables are especially nutritious. Examples include spinach, carrots, peaches, and berries. Eat a variety of grain products every day. Include whole-grain foods that have lots of fiber and nutrients. Examples of whole grains include oats, whole wheat bread, and brown rice. Eat fish at least 2 times each week. Oily fish, which contain omega-3 fatty acids, are best for your heart. These fish include tuna, salmon, mackerel, lake trout, herring, and sardines. Stay at a healthy weight by balancing the amount of calories you eat with the activity you do every day. If you want to lose weight, increase your activity level to burn more calories than you eat.

Eat foods low in saturated fat and cholesterol. Try to choose the following foods:

- Lean meats and meat alternatives like beans or tofu
- Fish, vegetables, beans, and nuts
- Nonfat and low-fat dairy products
- Polyunsaturated or monounsaturated fats, like canola and olive oils, to replace saturated fats, such as butter

Read food labels and limit the amount of trans fat you eat. Trans fat is found in many processed foods made with shortening or with partially hydrogenated or hydrogenated vegetable oils. These foods include cookies, crackers, chips, and many snack foods.

Limit sodium intake to less than 2,300 mg of sodium a day (about one teaspoon). Choose and prepare foods with little or no salt.

Limit alcohol intake to 2 drinks a day for men and 1 drink a day for women.

Limit drinks and foods with added sugar.

# Document History – Changes compared to previous final version of SAP

Date	Time point	Reason for update	Outcome for update	Section and title impacted (Current)
09- Dec- 2019	Prior to FPFV	Creation of final version	N/A - First version	NA

# List of abbreviations

ACR	Albumin-creatinine ratio
AE	Adverse event
ALP	Alkaline phosphatase
ALT	Alanine transaminase
ANCOVA	Analysis of covariance
APTT	Activated partial thromboplastin time
AST	Aspartate transaminase
ATC	Anatomical Therapeutic Classification
BMI	Body mass index
CI	Confidence interval
CSR	Clinical study report
CTCAE	Common Terminology Criteria for Adverse Events
CV	Coefficient of variation
DMC	Data monitoring committee
eCRF	Electronic case report form
eGFR	Estimated glomerular filtration rate
EOS	End of study
EOT	End of treatment
FAS	Full analysis Set
FGF	Fibroblast growth factor
GGT	Gamma glutamate transaminase
HA	Hyaluronic acid
HDL-C	High density lipoprotein cholesterol
IL	Interleukin
INR	International normalized ratio
ITT	Intent-to-treat
LDL-C	Low density lipoprotein cholesterol
LLOQ	Lower limit of quantification
MAR	Missing at random
MedDRA	Medical dictionary for regulatory activities
MMP	Matrix metalloproteinase

Novartis SAP	For business use only	Page 7 CLJN452D12201C
MMRM	Mixed model repeated measures	
MRI	Magnetic resonance imaging	
NAFLD	Non-alcoholic fatty liver disease	
NAS	NAFLD activity score	
NASH	Non-alcoholic steatohepatitis	
OCA	Obeticholic acid	
PCR	Protein-creatinine ratio	
PT	Preferred term / Prothrombin time	
RAN	Randomized set	
RNA	Ribonucleic acid	
SAE	Serious adverse event	
SAF	Safety set	
SAP	Statistical analysis plan	
SCR	Screened analysis set	
SD	Standard deviation	
SMQ	Standardized MedDRA Query	
SOC	System organ class	
TBL	Total bilirubin	
TD/EOT	Treatment discontinuation / End of treatment	
TFLs	Tables, figures, listings	
TIMP	Tissue inhibitors of metalloproteinases	
TT	Thrombin Time	
ULN	Upper limit of normal range	
ULOQ	Upper limit of quantification	
VAS	Visual analogue scale	
VLDL-C	Very low density lipoprotein cholesterol	
WHO	World Health Organization	

# 1 Introduction

The purpose of this Statistical Analysis Plan (SAP) is to provide details on the implementation of analyses outlined in section 12 of the study protocol and to be reported in the core Clinical Study Report (CSR).

Analyses based on this SAP will be executed after all patients complete the study.

Data analyses for Data Monitoring Committee (DMC) meetings will be specified in a separate DMC SAP.

# 1.1 Study design

[figure not shown]
This is a randomized, double-blind, parallel-group, multiple-arm study to assess the efficacy, safety and tolerability of tropifexor and licogliflozin combination therapy compared to each monotherapy in patients with non-alcoholic steatohepatitis (NASH) and advanced fibrosis.

The study consists of 1) a screening period, 2) a treatment period starting from randomization on Day 1 and running to Week 48, and 3) a follow-up period of 4 weeks after the last dose of study treatment. The screening period starts from the time of the signing informed consent and continues for up to 8 weeks when all inclusion/exclusion criteria have been evaluated and all baseline assessments have been performed. The study duration from first dose of study medication is 52 weeks. The total duration of participation may be up to 60 weeks.

Approximately 210 patients with NASH and F2-F3 fibrosis will be randomized in a 1:1:1 ratio to one of the following treatments:

- Arm A: tropifexor + licogliflozin combination therapy,
- Arm B: tropifexor monotherapy,
- Arm C: licogliflozin monotherapy

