12.4.2 Statistical model, hypothesis, and method of analysis

The main goal of the study is to reveal the efficacy of the combination therapy (tropifexor + licogliflozin) compared with placebo in the two primary endpoints, so the two tests of combination therapy vs. placebo (one for each endpoint) will be conducted first. The study will be considered successful if at least one of these two tests passes with statistical significance. An overall two-sided 5% (one-sided 2.5%) alpha is adopted to the study and is splitted evenly to the two primary endpoints. In addition to the comparison between combination therapy and placebo, another four pairwise comparisons may be evaluated for each primary endpoint, rendering a total of ten ([1+4]*2=10) potential comparisons. Each primary endpoint will have its own branch of tests and may pass its alpha to the other branch from its last two tests. Under each branch, the two monotherapies (LJN452 and LIK066) will be compared with placebo after the combination treatment shows superiority over placebo with significant evidence. If one of the monotherapy vs. placebo tests succeeds, then it will pass its alpha to the corresponding combination vs. monotherapy test. An alpha recycling graph (Bretz et al 2009) is presented in Figure 12-1 below to illustrate the test relationship.

Figure 12-1 An alpha recycling graph

Within each primary endpoint branch, five comparisons may be evaluated in the following levels:

- Combination vs. placebo
- Tropifexor (LJN452) vs. placebo; licogliflozin (LIK066) vs. placebo
- Combination vs. tropifexor (LJN452);
- Combination vs. licogliflozin (LIK066);

Since there are two primary endpoints, a total of ten comparisons may be tested.

The comparisons are based on the four arms of the study: one combination therapy arm, two monotherapy arms and one placebo arm. The proportions of histological responders in these four arms are assumed following binomial distributions (n, p). The sampling distribution of the difference $\hat{p}_{m_{_i}} - \hat{p}_{m_{_j}}$ will be asymptotically normal with mean $p_{m_{_i}} - p_{m_{_j}}$ and variance $\frac{p_{m_i}(1-p_{m_i})}{n_{m_i}} + \frac{p_{m_j}(1-p_{m_j})}{n_{m_j}}$, where *m* is the index of the primary endpoint (m = A if the

Novartis	Confidential
Amended Protocol Version 02 (Clean)	

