Combination vs. placebo (test 1, k = 1, i = Cmb, j = Plc)

Tropifexor (LJN452) vs. placebo (test 2, k = 2, i = LJN, j = Plc); licogliflozin (LIK066) vs. placebo (test3, k = 3, i = LIK, j = Plc)

Combination vs. tropifexor (LJN452) (test 4, k = 4, i = Cmb, j = LJN); combination vs. licogliflozin (LIK066) (test 5, k = 5, i = Cmb, j = LIK)

There are ten potential tests to be performed for the two primary endpoints (five for each primary endpoint), and it is important to control the overall Type I error rate for these tests. The alpha recycling graph presented in Figure 12-1 shows how alpha transfers among them. If the data fails to reject the null hypothesis of a test, then the alpha of that test will not be passed to others. This restriction ensures the control of overall Type I error rate. Again, for the primary

Confidential

Amended Protocol Version 02 (Clean) Protocol No. CLJN452D12201C endpoints, the overall alpha is set at two-sided 5%. A logistic regression model with the logit of probability for histological response as the dependent variable, treatment groups as the main effect, baseline fibrosis stage and T2DM (No/Yes) as explanatory variables, and the baseline BMI as a covariate will be utilized to test the hypotheses at each step. While this model will be the typical logistic regression in most cases, it should be set as the Firth logistic regression if some arm (such as the placebo) has a low response rate, as the Firth method returns less biased results for data with rare events. The null hypothesis of *k*th test, if executed, will be rejected if the p-value for the coefficient of treatment effect in the *k*th comparison is less than or equals to its corresponding alpha. If no alpha is passed to a specific comparison, then its corresponding test will not be performed and p-value will not be calculated. More statistical specifications of the model will be described in the statistical analysis plan (SAP).

The number and percentages of histological responders at week 48 in FAS will be summarized by treatment groups. The difference between the treatment of interest and the alternative treatment will be presented along with 95% confidence interval calculated based on the normal approximation for distribution of the difference between two binomial random variables.

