# 2.5.1 **Primary endpoint**

The primary endpoint is the proportion of patients experiencing histological response, which is defined as resolution of NASH (absence of ballooning with no or minimal inflammation by histology) and no worsening of fibrosis OR improvement in fibrosis by at least one stage without worsening of NASH (worsening of hepatocellular ballooning or lobular inflammation) at week 48 compared with baseline. The criteria for resolution of NASH (absence of ballooning with no or minimal inflammation by histology) and other changes in histologic endpoints are further detailed in Section 5.3.11.

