# 2.5.2 Statistical hypothesis, model, and method of analysis

To demonstrate improved efficacy of tropifexor+licogliflozin in combination, the response rate in the combination arm will be compared with each monotherapy arm. A one-sided test ( $\propto$ =0.05) of statistical superiority is planned for each comparison. A stepwise gatekeeping hierarchical test procedure, in which the second test is only performed if the first null hypothesis is rejected, will be adopted to maximize the power for the first test while still maintaining a strong control of family wise type 1 error rate (FWER-1) at 0.05.

The hierarchical testing will be performed in the following sequence.

- 1. Combination vs. licogliflozin (LIK066)
- 2. Combination vs. tropifexor (LJN452)

The order of the hierarchical tests is determined under a preliminary assumption that tropifexor, by targeting the Farnesoid X receptor that directly modulates liver inflammation and fibrosis associated with NASH, could potentially be more effective than licogliflozin hence results in smaller add-on effect of the combination when used as the reference in the comparison. If external data newly available during the study warrants different assumptions, the order of tests could be switched before the study unblinding without inflation of the FWER-1.

For these two tests on the same endpoint and sharing a common comparator (combination arm), the hierarchical testing approach also allows an intrinsic adjustment of the correlation between them for the power of the second test.

The proportions of histological responders in the three treatment arms are assumed following binomial distributions (**n**, **P**) and the sample distribution of the difference  $p_1-p_{2i}$  will be asymptotically normal with mean P1-P2i and variance P1\*(1-P1)/n1 + P2i\*(1-P2i)/n2i., where

 $i \in \{1, 2\}$  ~ the level of the hierarchical test

 $\mathbf{P} = (P_1, P_{21}, P_{22}) \sim$  True probabilities of histological responses after 48 weeks of treatment with the combination, licogliflozin and tropifexor respectively

Novartis	For business use only	Page 21
SAP		CLJN452D12201C

 $\mathbf{n} = (n_1, n_{21}, n_{22}) \sim \text{Number of patients in the combination, licogliflozin and tropifexor groups respectively in the study}$ 

 $\mathbf{p} = (p_1, p_{21}, p_{22}) \sim$  Proportion of histological responders observed in the study after 48 weeks of treatment with the combination, licogliflozin and tropifexor respectively

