#### Table 3-1Placebo effects on histological responses

The response rates for the monotherapies are deemed less likely to exceed 30%. For the stepwise gatekeeping testing procedure adopted for primary analysis, total sample size of 210 (70:70:70) is chosen so that there is approximately 80% power for the first hypothesis test (combination vs licogliflozin) if the true add-on effect is 20% for combination therapy.

Table 3-2	Power under different assumptions of mono and combination therapy
	effect sizes

True response rate assumptions		Add-on effect size in 1 st	power of 1-sided hierarchical tests α=0.05		
Licogliflozin	Tropifexor	Combination	test	1 st test	Both tests
30%	30%	38%	8%	25%	12%
23%	23%	33%	10%	38%	22%
30%	30%	44%	14%	53%	34%
30%	30%	47%	17%	67%	52%
23%	30%	41%	18%	75%	34%
20%	20%	40%	20%	84%	75%
25%	25%	45%	20%	80%	69%
30%	30%	50%	20%	79%	67%
30%	30%	51%	21%	82%	72%
23%	30%	46%	23%	89%	60%

Power calculations were performed with simulations (n=100000) implemented in R 3.3.3, where the primary analysis in each simulated study was performed using z-tests of difference in proportions without continuity correction for simplicity.

The dropout rate of the study is anticipated to be around 10%. Because early termination and missing response data will be incorporated into the primary analysis with multiple imputations, no adjustment for early dropouts from study were implemented for the sample size calculations.

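### The only SAP supplied predates the placebo amendment and sets out a three-arm, composite-endpoint, one-sided 0.05 analysis that conflicts with protocol version 02

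*SAP*

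**What the plan says.** **SAP.** The document history has a single entry, 09-Dec-2019, for a first version. Section 1.1 reads: "Approximately 210 patients with NASH and F2-F3 fibrosis will be randomized in a 1:1:1 ratio to one of the following treatments", and the three arms are combination, tropifexor and licogliflozin. The definition of study treatment in Section 2.1.1 has no placebo group either. Section 2.5.1 states: "The primary endpoint is the proportion of patients experiencing histological response". Response there is a composite: "resolution of NASH (absence of ballooning with no or minimal inflammation by histology) and no worsening of fibrosis OR improvement in fibrosis", where the second part means a gain of one stage or more with NASH no worse. Under Section 2.5.2 the combination is compared with licogliflozin and then with tropifexor. A one-sided test at 0.05 "of statistical superiority is planned for each comparison", with "strong control of family wise type 1 error rate (FWER-1) at 0.05". Section 2.6 adds four key secondary tests, opened only if both composite tests succeed. Section 1.1 also allows for the SAP to be amended after a protocol amendment.

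**Protocol version 02.** Section 6.1.3 assigns 380 participants to four arms, one of them placebo. Section 12.4 has two primary endpoints: fibrosis improvement without worsening of NASH, and NASH resolution without worsening of fibrosis. Section 12.4.2 says: "An overall two-sided 5% (one-sided 2.5%) alpha is adopted to the study", divided evenly between the two endpoints. Combination versus placebo is tested first, and success on either endpoint makes the study successful. The composite is the key secondary endpoint (Tables 2-1 and 12-1).

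The protocol leaves further detail to the SAP. On the model it says: "More statistical specifications of the model will be described in the statistical analysis plan (SAP". Section 12.4.4 leaves imputation details to the SAP, and Section 12.4.5 leaves it the sensitivity analyses.

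**The concern.** SAP Section 1 gives the document's purpose as implementing Section 12 of the protocol. A statistician who follows the protocol's cross-references to this SAP does not find gaps. The SAP gives contrary rules on arms, comparator, primary endpoint, error rate, response definition, safety set and intercurrent events.

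An analyst who ran the SAP as written would produce no placebo comparison and would leave placebo patients out of the safety tables. If the conflict is still open at unblinding, someone must choose between two sets of rules with the data in view. The choice of endpoint, error rate and responder definition would then look post hoc, however sound it was.

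**Working it through.** **1. Dates.** SAP: 09-Dec-2019. Amendment 01, which added placebo, split the primary endpoint and changed the error rate: 18-Sep-2020. Amendment 02: 30-Apr-2021. The SAP's own list of changes from protocol (Section 4) therefore mentions none of this.

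**2. Counting tests.** The protocol has 2 endpoints × 5 comparisons = 10 primary tests. Three of each five are against placebo (combination, tropifexor, licogliflozin), so 2 × 3 = 6 are placebo tests. The SAP's six tests, H1 to H6, are all combination versus a monotherapy, so none of the 6 is present. The other 10 − 6 = 4 are the SAP's H3 to H6, run only if H1 and H2 on the composite are both rejected.

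**3. Error rate.** SAP family-wise: one-sided 0.05. Protocol family-wise: two-sided 0.05, that is, one-sided 0.025. Ratio: 0.05/0.025 = 2.

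**4. Each plan's power reproduces for its own design.**
- *SAP Table 3-2* ("power of 1-sided hierarchical tests α=0.05"), n = 70 per arm. Power = Φ{[(p2 − p1)√n − z√(2p̄(1 − p̄))] / √(p1(1 − p1) + p2(1 − p2))}, with z = 1.645. For 30% vs 50%: (0.20 × 8.367 − 1.645 × 0.6928)/0.6782 = 0.787, giving 78.4% (stated 79%). For 25% vs 45%: 80.4% (stated 80%). For 20% vs 40%: 83.2% (stated 84%). At two-sided 0.05 the first of these falls to 67.9%, so the table does rest on one-sided 0.05.
- *Protocol Tables 12-4 and 12-5.* Simulation of 200,000 trials used the Table 12-3 rates, correlation +0.5, unpooled z-tests without continuity correction, and two-sided 0.025 per endpoint. At 95 vs 95 it gives 54.8%, 71.7% and, for at least one endpoint, 80.1% (stated 0.55, 0.72, 0.80). At 140 vs 80, at least one endpoint gives 84.8% (stated 0.85).

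Neither calculation is wrong. They belong to different trials.

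**5. The SAP's gate under the protocol's rates.** Assume the +0.5 correlation holds in every arm. The composite rate is pA + pB − pAB, with pAB = pA·pB + 0.5√(pA(1 − pA)pB(1 − pB)).
- Combination: 0.35 + 0.25 − (0.0875 + 0.1033) = 0.409.
- Monotherapy: 0.30 + 0.20 − (0.0600 + 0.0917) = 0.348.

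At one-sided 0.05 the SAP's first test then has about 18% power at 70 vs 70 and 22–23% at 140 vs 80. Both composite tests succeed in about 8–10% of trials, so H3 to H6 would seldom be reached.

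**6. Other rules that differ.**

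| Rule | SAP | Protocol version 02 |
|---|---|---|
| Safety set | 2.2: leaves out anyone who took only matching placebo | 12.1: everyone with at least one dose, by treatment received |
| Worsening of NASH | 5.3.11.2: a rise in lobular inflammation or ballooning | 12.4.1: a rise in either of these or in steatosis |
| Intercurrent events | 2.5: while-on-treatment and hypothetical, with imputation | 12.4.3: mainly treatment policy or composite (non-responder) |

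Taken literally, the first row removes the whole placebo arm, planned at 80, from the safety analyses. The second changes who counts as a responder on the first primary endpoint. Under the third, a participant who stops treatment before Week 24 is imputed by the SAP but is a non-responder in the protocol.

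**The case against.** The strongest reply is that this is a dated document and not a wrong one. The SAP was written before the first patient visit, for the design of the time, and foresees its own amendment. The 2021 protocol speaks of the SAP in the future tense, and the Amendment 02 rationale says that details of the corrected NASH definition will go into it. That points to a later SAP, which may exist outside the documents supplied. The deferral is also limited: protocol Section 12.4 itself gives the hypotheses, test order, covariates, Firth rule, imputation method and intercurrent-event strategies. All of this stands. It places the fault in the SAP supplied, but it does not remove the contrary rules or say which document governs.

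A reader might infer three stronger things that the documents do not support.
- *That the main question goes untested.* Protocol 12.4.2 prespecifies combination versus placebo on both endpoints. The SAP's model, fitted to three arms, could not be applied unnoticed to four-arm data.
- *That the SAP's error rate is four times too loose (0.05 against 0.0125).* One-sided 0.0125 is the protocol's starting level for combination versus placebo, a test the SAP lacks. The tests common to both documents receive alpha through Figure 12-1, whose weights are not shown. Only the family-wise comparison is like for like.
- *That placebo contrasts are owed in every table.* The protocol asks only for by-treatment estimates for ALT, AST and GGT, and by-treatment safety summaries.

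**Conclusion.** The conflict is confirmed, and it must be resolved before database lock and unblinding. The SAP supplied omits 6 of the protocol's 10 primary tests, demotes the other 4 to gated key secondary tests, and allows twice the protocol's one-sided family-wise error. It also departs from the protocol on the safety set, NASH worsening and intercurrent events.

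These conclusions rest on the text of the two documents and need no assumption about treatment effects. Only the 18–23% and 8–10% figures depend on the protocol's assumed response rates and on its correlation holding in each arm. Whether a later SAP exists cannot be told from what was supplied, so the finding concerns this SAP and not the sponsor's final intentions.

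**What to change.** Before database lock and unblinding, amend SAP Sections 1.1–1.2, 2.1.1, 2.2, 2.5–2.8, 3 and 5.3–5.4 to protocol version 02, or identify the later SAP that already does this. The amended text should carry:
- four arms, with placebo in the study-treatment definition and the safety set;
- the two primary endpoints at two-sided 0.025 each, with the alpha graph, and the composite as key secondary;
- the contrasts the protocol asks for;
- the protocol's definition of NASH worsening and its intercurrent-event strategies.

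In the same amendment, resolve two points on which the protocol disagrees with itself, so that they are not carried over. Section 4.1 still names the composite as the primary endpoint. Section 12.4.3 counts participants with no Week 48 biopsy as non-responders, while Section 12.4.4 uses an early-termination biopsy taken after at least 24 weeks of treatment and otherwise imputes missing endpoints and endpoints after intercurrent events.

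Until the amendment is issued, state that protocol Section 12 governs. The cost is one SAP amendment, with no effect on trial conduct or sample size.
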